#### 5.7 Withdrawal of Subjects

**Study Completion or Discontinuation and Breaking the Blind:** Study completion refers to an enrolled participant having completed the full 12 weeks at the constant study drug maintenance dose level. Study discontinuation refers to premature exit from the study by a participant, either voluntarily or at the recommendation of the clinician prescriber.

The clinician prescriber may authorize premature discontinuation of participant involvement for safety reasons or other concerns, discovery of use of excluded medications, or intolerable worsening of existing HAs. Participants who begin any new scheduled prophylactic headache treatment during the study will be discontinued.

The team at the study site will triage any participant to emergency care, mental health support, or clinical care/follow-up as appropriate at any time during the study.

Safety concerns leading to termination of participant involvement may include but are not limited to pregnancy, development of an intolerable adverse reaction to the study drug or inactive constituents, development of an acute serious medical condition, or development of an unstable psychiatric condition. Study discontinuation will also occur if there are unacceptable adverse effects on the lowest study drug dose (1 mg qhs). For the purpose of maintaining participant safety, physical and neurological examinations and urine pregnancy test verification will only be conducted via approved telehealth applications or during an in-person visit. If a participant is unable to comply with these restrictions, then they will be withdrawn or excluded from the study for safety reasons. The reasons for early withdrawal or discontinuation will be recorded. For participants who are prematurely discontinued from the study after randomization, we will attempt to schedule an early termination visit. At this visit, all end-of-study procedures will be obtained in order to include these measures in the Intent-to-Treat (ITT) analyses.

The blind will be broken for participants who are discontinued from the study, whether by voluntary withdrawal or on the advice of the clinician prescriber, on the date of discontinuation.

All reasons for breaking the blind will be recorded, as will the name of the person breaking the blind.

For participants completing the entire trial, the blind will be broken at the end of the 12-week Visit. Maintaining the blind until all participants have completed the protocol and the database has been locked would be ideal; however, previous studies have shown that optimal safety and follow-up patient care argues in favor of breaking the blind for each person when they complete the trial. All participants will be given the option of treatment with open-label prazosin after study completion (an important condition for recruitment, given that prazosin is clinically available). The appropriate and safe method for initiating open-label prazosin differs depending on whether the participant had been randomized to prazosin or placebo. For those randomized to prazosin and having improvement in their HAs, subsequent open-label prazosin should be kept at the maximum achieved dose, and may be titrated further upward, if additional clinical benefit might be obtained. On the other hand, participants randomized to placebo will require titration to effect, as per the study titration schedule, initiated at a low dose (1 mg) to avoid the risk of first-dose hypotension.

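### Section 5.7 breaks the blind at discontinuation without requiring the early termination assessments to come first, so some self-reported secondary outcomes can be collected unblinded

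*Combined protocol and SAP*

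**What the plan says.** Section 5.7 holds two rules for participants who stop early.

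- **Termination visit.** For those discontinued after randomization, "we will attempt to schedule an early termination visit". Its purpose is stated: "At this visit, all end-of-study procedures will be obtained in order to include these measures in the Intent-to-Treat (ITT) analyses". Section 5.5, under the steady-dose visits, repeats that a termination visit covering the week-12 procedures is held where possible. It sets no deadline.
- **Code break.** "The blind will be broken for participants who are discontinued from the study". The timing is the same for either route out: "whether by voluntary withdrawal or on the advice of the clinician prescriber, on the date of discontinuation". On documentation: "All reasons for breaking the blind will be recorded, as will the name of the person breaking the blind".

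The section defines the event as follows: "Study discontinuation refers to premature exit from the study by a participant".

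For completers the order is fixed: "the blind will be broken at the end of the 12-week Visit". The reason given is that "optimal safety and follow-up patient care argues in favor of breaking the blind for each person when they complete the trial". The same paragraph accepts that keeping the blind until database lock would be ideal.

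Section 5.6 analyses MIDAS at baseline and week 12 only, and HIT-6 at baseline and steady-dose weeks 4, 8 and 12. The schedule of study visits gives PSQI, ISI, PCL-5, PHQ-9, AUDIT-C and VR-12 the same three follow-up points as HIT-6.

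**The concern.** The two rules for discontinued participants are never put in order. A visit that staff still have to schedule for someone already discontinued can fall after the date on which the code is broken. If it falls on that date, the sequence within the day is open. The protocol therefore sets the safe order for completers and leaves it unset for dropouts, although both sets of values go into the same ITT comparison.

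The measures at stake are self-reports of disability, sleep, mood, PTSD symptoms, alcohol use and quality of life. Knowing the arm can change how such questions are answered, and the blind is there to prevent that. Section 5.6 deals with missing values, not with values observed after unblinding, so no planned analysis would show whether they matter.

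**Working it through.** **1. The plan's own figures.** Section 5.6 gives 111 completers (74 and 37), 80% power at an effect size of 0.57 with a two-sided 5% t-test, 30% dropout and 160 randomized. A noncentral t calculation with 74 and 37 gives power 0.801. 111 / 0.70 = 158.6, so 159, against 160 stated. Both reproduce.

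**2. Participants under the rule.** 0.30 × 160 = 48 dropouts, leaving 160 − 48 = 112 completers.

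**3. MIDAS (one follow-up value per person).** Let *a* be the proportion of dropouts who attend a termination visit after unblinding. The documents do not give *a*, so the values below are assumptions.

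Share = 48*a* / (112 + 48*a*)

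| *a* | Affected / total | Share |
|---|---|---|
| 10% | 4.8 / 116.8 | 4.1% |
| 25% | 12 / 124 | 9.7% |
| 50% | 24 / 136 | 17.6% |
| 75% | 36 / 148 | 24.3% |
| 100% | 48 / 160 | 30% |

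**4. Scales with three follow-up values.** Completers supply 3 × 112 = 336 values, assuming none is otherwise missing. The two extremes of dropout timing bound the share of all follow-up values.

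| *a* | All leave before week 4 | All leave after week 8 (2 × 48 = 96 blinded values added) |
|---|---|---|
| 25% | 12 / 348 = 3.4% | 12 / 444 = 2.7% |
| 50% | 24 / 360 = 6.7% | 24 / 456 = 5.3% |
| 75% | 36 / 372 = 9.7% | 36 / 468 = 7.7% |
| 100% | 48 / 384 = 12.5% | 48 / 480 = 10% |

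**5. How many dropouts have no blinded follow-up value on any of these scales?** Section 5.6 expects dropout across both titration (5 to 7 weeks) and the 12 steady-dose weeks. If it were uniform over time (an assumption), the proportion leaving before steady-dose week 4 is (5 + 4)/(5 + 12) = 9/17 = 53% to (7 + 4)/(7 + 12) = 11/19 = 58%, or about 25 to 28 of the 48. For them the termination value is the only follow-up on every scale in step 4 as well as on MIDAS.

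**6. Primary outcome.** It comes from the daily headache log. Entries before exit are made under the blind, and no section asks for entries after it.

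**7. Could affected values be found later?** Coded data keep the visit date (section 7.0), and section 5.6 plans to compare the timing of dropouts. Visits on a later day than discontinuation could therefore be flagged. Section 5.7 requires the reason for unblinding and the name of the person who broke the blind, but not the time, so same-day values could be separated only if a site happened to record it.

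**The case against.** The strongest reply is that section 5.7 can be followed safely as written. It defines discontinuation as exit from the study, and someone still attending a study visit has arguably not exited. It also describes the visit before the unblinding rule. On that reading the discontinuation date is the visit date, and assessing first and unblinding second complies. This stands as far as it goes: the text permits that order but does not require it, and the other reading is at least as natural.

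Harm also needs a chain of conditions that the documents do not establish: the visit takes place, it follows the code break, the participant is told the arm, and the answers shift. This too stands, and it limits the size of the point.

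A reader might infer more than the documents support:

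- **That termination data will be unblinded.** The text allows this but does not prescribe it, and it does not say who learns the assignment.
- **That the problem is confined to MIDAS.** Its exposure follows from the visit schedule; nothing shows its answers to be more easily swayed. Early dropouts have the same gap on the other scales.
- **That same-day values can never be separated.** The protocol does not require a time, which is different from none being recorded.
- **That 30% of MIDAS values will be affected, or that a bias or type I error rate follows.** The 30% needs every dropout to attend after unblinding. Any bias figure would rest wholly on an assumed shift in reporting.
- **That the headache-frequency result is compromised.** Step 6 of the working shows why this does not follow.

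**Conclusion.** The point holds as a gap in ordering, of minor to moderate weight. Followed literally, section 5.7 lets self-reported secondary outcomes be collected after unblinding, provided that discontinuation precedes the visit and the participant is told the assignment. MIDAS is exposed for every dropout. HIT-6, PSQI, ISI, PCL-5, PHQ-9, AUDIT-C and VR-12 are exposed in the same way for those who leave before steady-dose week 4, and less so for later leavers, who already have blinded values.

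The ceiling is 30% of final MIDAS values and 10% to 12.5% of follow-up values on the repeated scales, at the planned 30% dropout. The actual share may be well below this: section 5.6 attributes dropout mainly to reassignment or deployment, the visit is only attempted, and same-day assessments may in practice come first. Informative dropout, and the 3-month MIDAS recall period for those who leave early, are separate matters.

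**What to change.** In section 5.7:

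- State that, unless the clinician judges that safety or care needs earlier unblinding, the early termination assessments are completed before the blind is broken, as for completers.
- Set a limit, chosen by the sponsor, after which the blind may be broken if no termination visit takes place.
- Require the date and time of both the assessments and the unblinding to be recorded.
- State who is told the assignment.

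In section 5.6, keep all values in the ITT analysis and add one sensitivity analysis without values obtained after unblinding.

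**Cost.** A few sentences, one data field and one extra analysis. Some non-urgent dropouts would learn their assignment slightly later. The delay can be short, because section 5.5 already lets self-rated measures be sent out and returned remotely. That route is partial: the MoCA needs video or attendance, and the blood draw and pupillary reflex may be skipped when the participant cannot attend. The reason given for unblinding completers individually, safety and follow-up care, is met by the exception.

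At worst the sensitivity analysis rests on the 112 completers. That this exceeds the planned 111 is no particular comfort for MIDAS. The 80% power figure is for an effect size of 0.57, while section 5.6 cites 0.7 and 0.2 for MIDAS. The analysis should support the ITT result, not replace it.

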### 6.0 Reporting

Adverse event reporting will begin after the dispensing of the first dose of study drug.

**Serious adverse events (SAEs):** SAEs (defined as any untoward medical occurrence which may be related to study participation at any time during the study that results in subject death, is life threatening, requires hospitalization, or results in persistent or significant disability/incapacity), will be reported to the PI, or if not available, another clinician investigator immediately upon discovery. SAEs will be reported to the Madigan IRB and DCI per current Madigan policies. The Madigan research monitor and the DSMB will be notified of the submission. A copy of the report will also be sent to the VA Puget Sound IRB per VA guidelines.

**Adverse Events (AEs):** Unexpected, but not serious, AEs, which the PI determines are related or possibly related to research participation, will be reported to each IRB per local guidelines. The Madigan research monitor and the DSMB will be informed of the event. Expected adverse events, which are not serious and possibly related to research participation, will be reported to the Madigan and VA Puget Sound IRBs on the annual report.

**Unanticipated problems:** Involving breach of confidentiality or HIPAA violation or any other risk to the health or welfare of participants that the PI determines are related or possibly related will be reported to each IRB per local guidelines. The Madigan research monitor and the DSMB will be informed of the event.

All other adverse events or problems that the PI determines are unrelated to research participation will be reported to the Madigan IRB/DCI with the annual report.

A summary of all above reports will be sent to the Madigan and VA Puget Sound IRBs with the annual report. Departures from the protocol, which do not involve risks to volunteers or affect the scientific integrity of the study, will be reported annually to the Madigan and VA Puget Sound IRBs. Deviations, which involve unanticipated problems involving risks to volunteers or others, will be reported promptly, using the procedures described in reporting of adverse events above.

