# 5.0 Study Procedures

# 5.1 Study Design

**Overview:** The study is a prospective double-blind placebo-controlled RCT to evaluate the efficacy of prazosin for prophylactic treatment of frequent persistent HAs following blast and/or impact mTBI in a convenience sample of male and female SMs and Veterans aged 18 and older who have a history of mTBI with chronic PTHAs and who meet inclusion/exclusion criteria as described further below. We anticipate enrollment of 228 participants to achieve 160 randomized -- an average of approximately 4-5 participants randomized per month divided approximately equally across the 2 sites.

All study procedures are investigational; none are standard of care. The total trial length is up to 24 weeks, including a 5-week Preliminary Screening Period during which the participant will keep a HA log, eligibility for randomization will be determined, and baseline data (including 1 week of sleep/activity monitoring using actigraphy and keeping a sleep log) will be collected; a 5-7week Titration Period, during which optimal dose will be determined; and a 12-week Steady-Dose Period, as detailed in section 5.5 below and in the schedule of study visits table.

Participants who remain eligible after the Preliminary Screening period will be randomly assigned 2:1 to prazosin or placebo and will then begin the study drug dose Titration Period. During the Titration Period, the dose of study drug will be gradually increased to a maximum dose of 5 mg each morning and 20 mg each evening or to the maximum tolerated dose. Once the maximum (or maximum tolerated) dose has been attained, the participant will continue on this dose for 12 weeks. Evaluations to be performed are described in section 5.5 below and on the Schedule of Study Visits table.

**Investigational Drug:** This study will be conducted using the drug, prazosin, which has been approved by the FDA for treatment of hypertension but is being used off-label for investigational purposes in this study. Prazosin and indistinguishable placebo will be obtained from commercial sources. Investigational pharmacists at each study site will procure the study drug. Study drug may be stored at room temperature. Unused drug will be disposed of by the investigational pharmacists once notification has been made by the PI that the study has been completed.

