**Risk Management and Emergency Response:** Evaluation for adverse effects and review of concurrent medications will be completed at all study visits. Participants are asked about suicidal ideation at each in-person visit. If endorsed, participants will be assessed as to their level of risk and the level of care required to keep them or others from harm. If a participant requires inpatient treatment in order to prevent harm or is found to have symptoms of disorganized thought processes secondary to psychosis, mental health personnel will be notified immediately to assist with appropriate triage and referral. Vital signs, including orthostatic blood pressure (BP) and heart rate (HR) will be performed at all study visits. Systolic and diastolic BP and HR will be obtained following 10 minutes of rest, and repeated following 2 minutes of standing. Occurrences of lightheadedness, dizziness on standing, palpitations, drowsiness, nausea, nasal congestion, peripheral edema, worsening of HA, and other adverse effects will be rated by the clinician. For vital signs parameters, unacceptable side effects will include resting hypotension (systolic BP<100 mm Hg) and clinically meaningful hypotension (20 mm Hg or more drop in systolic BP accompanied by dizziness, lightheadedness, or syncope).

For participants taking other antihypertensive medications, their primary care provider will be informed of clinically significant BP reductions at any time during the study, to allow adjustment of the participant's antihypertensive regimen. As a further precaution, male subjects will be advised to sit on the toilet for urination the first two nights to avoid orthostatic hypotension secondary to micturition syncope.

Safety monitoring is based on long-term clinical experience with prazosin. Prazosin was first introduced in 1976 under the trade name Minipress (Pfizer) for clinical management of hypertension, and later became widely prescribed for urinary outflow obstruction secondary to benign prostatic hypertrophy. It has been safely prescribed to large numbers of middle-aged and older people over the past 40 years. The following information regarding the side effect profile and safety record of prazosin is a synopsis from the Minipress package insert: "The most important adverse effect to be considered when prescribing

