- The "as-needed" (prn) use of any non-exclusionary medications is allowed; however, such use must be discussed with a clinician prescriber and documented.
- The use of butalbital in any form within 4 weeks of beginning the Preliminary Screening Period (P1) through the end of the participant's study involvement is exclusionary.
- Participants who have been taking trazodone will undergo a 2-week washout period before the Preliminary Screening Period (P1 visit). Combining prazosin and trazodone may increase the risk of priapism. We have decided to begin the washout period before the Preliminary Screening Period in order to remove any confounding variables while on the headache log and actigraphy.
- Sildenafil (Viagra), tadalafil (Cialis), vardenafil (Levitra), and avanafil (Stendra) will not be permitted during the study drug dose Titration Period, because of increased risk of hypotension in combination with alpha-1 blockers, but will be allowed at half the usual starting dose following the study drug dose Titration Period, per VA prescribing guidelines.
- Use of supplements containing nitrates and supplements containing stimulants (such as ephedra) are exclusionary in the two weeks prior to initial screen (P1) visit and prohibited throughout the study. Participants who take these supplements will be asked to discontinue them for a minimum of two weeks before the Preliminary Screening Period (P1 visit).
- Use of prescribed stimulants (such as amphetamine or dextroamphetamine containing medications) is exclusionary in the 2 weeks prior to the initial screen (P1) visit and prohibited throughout the study. Participants who take these medications will be asked to discontinue them for a minimum of 2 weeks before the Preliminary Screening Period.
- Participants may also be excluded at the discretion of PI or study clinicians if they appear to be unsuitable for this research study for a reason not detailed here. This may include risk factors for COVID-19 infection that are considered to present excessive risk given background local COVID-19 transmission rates and available safety protocols at the time of evaluation.

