Participants will begin keeping the HA log at the beginning of the Preliminary Screening period and will continue for the duration of the Preliminary Screening Period. If they are determined to be eligible to continue in the study (see below), they will continue keeping the HA log for the remainder of the study phases, including the Titration and Steady-Dose Periods. The Screening HA log data will be used to both confirm that participants are eligible to continue into the Titration Period of the study and to provide baseline data that will be used for comparison with data from the Steady-Dose Period to address the primary and secondary outcome measures.

Participants will be called for a brief telephone visit during weeks 1 and 3 of the screening period. The calls will answer any questions about the HA log keeping and encourage compliance. Medication and health changes will be queried.

At the end of 4 weeks of HA log keeping, the HA log will be reviewed at the Final Screening Visit to determine participant eligibility to continue in the study. Eligibility criteria include 8 or more HA days in the 4-week period of log keeping. A HA day is defined as a calendar day in which the participant had HAs that either 1) lasted for 4 or more hours and reached a pain intensity of moderate to severe at any point during the HA or 2) were of any severity or duration if the participant took a medication or other agent (e.g., caffeine) in an effort to stop or treat a headache. HA log entries must be recorded for at least 80% of the days, and there must be no exclusionary medication or supplement use. Vital signs (BP and HR) will be checked to ensure absence of orthostatic hypotension. Participants will be scheduled for the Baseline Visit, which will optimally occur 7 days later, but not more than 14 days later. During the interim week between the Preliminary Screening Period and the Baseline Visit, participants will

continue keeping the HA log and will undergo baseline sleep/activity monitoring with 7 days of actigraphy and keeping a sleep diary.

If it is found that a potential participant does not meet the inclusion criteria, follow-up care will be coordinated when needed with the appropriate clinic at the study site, either Madigan or VA Puget Sound.

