After the above procedures are completed, participants will receive the study drug and will be instructed in dosing procedures and safety precautions to prevent potential adverse effects. They will be instructed to continue keeping the daily HA Log, and to start taking the study drug that evening. The prazosin titration schedule is summarized in the Study Drug Titration table. The dosing regimen is based on our experience using prazosin to treat combat-trauma PTSD. The starting dose will be a 1 mg capsule of study drug (prazosin or identical placebo) qhs for the first 2 nights. Then the dose will be increased to 2 mg qhs. For the first week, the study drug will be taken while the participant is in bed for the night, to avoid orthostatic syncope, an uncommon but recognized "first-dose" effect of prazosin. The first-dose effect is avoidable by starting study drug with a low dose, then titrating upward gradually.

The participant will be asked to call the study team the morning after the first dose to make sure there was no occurrence of postural dizziness. The participant will be given a 24-hour contact number in case of adverse events any time the dose is increased.

Dose Titration Visits: Participants will be seen at each dose increase beginning after completion of the first week, according to the titration schedule summarized in the Study Drug Titration Schedule table, to evaluate for adverse effects; record any new medications and interval medical problems; monitor resting and standing BP and HR; confirm that the HA Log is current; determine whether proceeding to the next step of the dose titration is appropriate; and to provide additional study drug for the scheduled dose increase or dose maintenance. A dose increase will occur if the participant does not have unacceptable side effects. Clinical judgement may be used to maintain or decrease the dose as necessary. Dose titration visits are scheduled at the completion of Titration weeks 1 to 5.

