| ASC  | Х                    |                |                              |                |                                 |          |                               |                       |          |                     |                     |                | Х               |
| UPSIS-12M  |                      |                |                              |                |                                 | Х        |                               |                       |          |                     |                     |                | Х               |
| Actigraphy and Sleep Diary   |                      |                |                              |                | $\mathbf{X}^{c}$                |          |                               |                       |          |                     |                     | X c |                 |
| Medications review   |                      | Х              | Х                            | Х              | Х                               | х        | х                             | Х                     | Х        | Х                   | Х                   | Х              | Х               |
| Dispense/Review Headache Log   | Х                    | Х              | Х                            | Х              | Х                               | Х        | х                             | Х                     | Х        | Х                   | Х                   | Х              | Х               |
| Review side effects/adverse events   |                      |                |                              |                |                                 |          | x                             | Х                     | Х        | Х                   | Х                   | Х              | Х               |
| Dispense and/or return study drug  |                      |                |                              |                |                                 | Х        | ×                             | Х                     | Х        | Х                   | Х                   |                | Х               |
| Approximate length of visit (hrs)  | 3                    | 1/4            | 1⁄2                          | 1/4            | $1 \ \%$                        | с        | 1/2-3/4                       | 1/2-3/4               | $^{1/2}$ | З                   | З                   | 1/4            | З               |

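### Adverse-event reporting opens only at first dispensing, so events from study-directed drug withdrawal and pre-dose procedures are not reported as AEs or SAEs, and no pre-dose rating of the side-effect symptoms is scheduled

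*Combined protocol and SAP*

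**What the plan says.** Section 6.0 opens with the rule "Adverse event reporting will begin after the dispensing of the first dose of study drug". Section 5.5 fixes that moment at the end of the Baseline Visit: "After the above procedures are completed, participants will receive the study drug".

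Three other places bear on it.

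- Section 5.1, under risk management: "Evaluation for adverse effects and review of concurrent medications will be completed at all study visits". The same paragraph lists symptoms for the clinician to rate, among them dizziness on standing, lightheadedness, drowsiness, nausea, palpitations and worse headache.
- The schedule of visits in section 5.5: the row "Review side effects/adverse events" is empty at P1, P1.5, P2, P2.5, P3 and T1, and is marked from T2 onward.
- Section 6.0 again: the SAE definition covers possibly participation-related events throughout the study, with no start date.

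Before dispensing, the plan alters some participants' medication. For trazodone, section 5.4 says: "Participants who have been taking trazodone will undergo a 2-week washout period before the Preliminary Screening Period (P1 visit". For prescribed stimulants it says: "Participants who take these medications will be asked to discontinue them for a minimum of 2 weeks before the Preliminary Screening Period".

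**The concern.** The study can cause harm before its AE window opens. It asks some participants to stop a sleep medicine or a stimulant, and section 5.4 justifies the timing of the trazodone washout partly by the wish for clean headache-log and actigraphy data. At P1 it administers a psychiatric interview and a combat-exposure scale; section 5.1 names distress from such instruments as a foreseeable risk. At T1 one site draws about 65 ml of blood before drug is handed over.

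Classification as an AE or SAE triggers the AE and SAE reporting paths of section 6.0. A hospitalisation after a study-directed withdrawal has no clear place in them, in a population for which section 2.0 cites a suicide mortality hazard ratio of 1.34 for migraine. The two sites report under separate IRBs (section 4.0) and could read the conflicting text differently.

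The second issue is interpretation. Section 5.5 makes each dose increase depend on the absence of unacceptable side effects. If the symptom list is first rated at T2, dizziness or nausea already present after mTBI can be entered as a new effect of study drug.

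**Working it through.** **The plan's own timeline.** Inputs: 4-week headache log and 1-week sleep monitoring (abstract), titration of 5 to 7 weeks and steady dose of 12 weeks (section 5.1). The maximum is 4 + 1 + 7 + 12 = 24 weeks, which matches the stated total. Section 5.1 gives the screening part as "a 5-week Preliminary Screening Period during which the participant will keep a HA log", consistent with 4 + 1 = 5.

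**Drug stop to start of AE reporting.** The washout is at least 2 weeks before P1, and P1 to P3 takes 4 weeks. Section 5.5 describes the Baseline Visit that follows P3 as one "which will optimally occur 7 days later, but not more than 14 days later".

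- Nominal: 2 + 4 + 1 = 7 weeks.
- With the 14-day gap: 2 + 4 + 2 = 8 weeks.
- If the general 6-day visit window also applies to T1: 7 − 6/7 ≈ 6.1 weeks.

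P1 to dispensing alone is 4 + 1 = 5 weeks, or 4 + 2 = 6 with the longer gap.

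**Who is affected.** All 228 planned enrolees pass through screening. By plan 228 − 160 = 68 are never randomised, so they never enter the AE window. The share needing a washout is not stated.

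**The passages side by side.**

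| Source | Adverse effects before T2 |
|---|---|
| 5.1, risk management | evaluated at every visit |
| 5.5, schedule row | not marked, P1 through T1 |
| 6.0, opening rule | reporting not yet begun |
| 6.0, SAE definition | in scope throughout the study |

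The section 5.1 sentence pairs adverse effects with concurrent medications. The schedule marks its medications-review row from P1.5 through T1 but leaves the adverse-event row blank at the same visits, so it carries out only half of the sentence during screening.

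**Consent and washout.** Section 5.1 places the trazodone washout before the study starts. Section 5.4 places it before P1. The schedule puts consent at P1. Section 5.3 requires consent before any study procedure. Section 5.5 allows up to 6 weeks from the consent visit to the end of P1 procedures for stabilising medications. Together these do not settle whether consent comes first. If consent is signed only at P1, reporting from consent would cover 5 of the 7 nominal weeks and miss the 2 washout weeks.

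**The case against.** The strongest reply is that the safety net is wider than the opening rule of section 6.0. That section has a separate route for unanticipated problems, which covers other risks to participants' welfare that the PI judges related or possibly related. These go to each IRB, and the research monitor and DSMB are informed. Before dosing the plan also collects medical and psychiatric history, examination, SCID-5, orthostatic vital signs at P1, P2, P3 and T1, two calls asking about health changes, a suicidal-ideation question at each in-person visit, PHQ-9, PSQI, ISI, the daily headache log, and the NSI (apparently the Baseline row printed as ISN). Evaluating and reporting are different acts, so staff could evaluate at every visit and start reporting at dispensing.

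Much of this stands. A reader might infer that pre-dose harm goes unrecorded and reaches no oversight body; the documents do not support that. What remains is narrower. The unanticipated-problems route depends on PI judgment and does not make these events AEs or SAEs. The listed measures mostly begin at P1, after the washout. The distinction between evaluating and reporting removes neither the conflict between section 5.1 and the schedule nor that between the SAE definition and the opening rule.

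The blood-draw example is also thin: drug is dispensed later in the same visit, so delayed complications fall inside the window.

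**Conclusion.** The point holds as a gap in AE/SAE reporting and an inconsistency to reconcile. Study-directed withdrawal precedes the start of AE reporting by 7 weeks nominally and up to 8 with the longest P3-to-T1 gap. Events in that time, and from pre-dose procedures, are not reported as AEs or SAEs, and no pre-dose rating of the section 5.1 symptom list is scheduled. This rests on reading the opening rule of section 6.0 as governing both AEs and SAEs, and on the schedule row being blank through T1.

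Two further inferences are not supported.

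- A much longer interval, such as 2 + 6 + 4 + 2 = 14 weeks from adding the 6-week P1 allowance. That allowance exists partly for medication stabilisation, so the washout may already sit inside it, and the headache log starts at the beginning of screening rather than after the allowance ends.
- Bias between arms. The missing rating affects both blinded arms alike. It weakens the attribution of individual symptoms and the reading of absolute event rates, not the randomised comparison in itself.

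This is a worthwhile, inexpensive improvement; it does not threaten the primary analysis.

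**What to change.** 1. In section 6.0, start AE and SAE reporting at signed consent, so that the opening rule agrees with the SAE definition and with section 5.1.
2. In sections 5.1, 5.3, 5.4 and 5.5, state that consent precedes any study-directed washout. Without this, step 1 may still miss the washout weeks.
3. In the schedule, mark "Review side effects/adverse events" at P1.5 through T1.
4. At T1, before the first dose, have the clinician rate the section 5.1 symptom list once. Later events can then be tabulated as new or worsened relative to that rating.

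The cost is protocol wording, a few schedule marks and one short rating at an existing visit; the screening calls already ask about health changes. If consent is currently signed at P1, participants needing a washout would have to consent earlier. Some screening events unrelated to drug will be recorded; tabulate them separately as pre-treatment so that they do not enter the on-drug rates.
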